6.1. Appendix 1: Demographic and Baseline Characteristics

Baseline characteristics will be summarized for the randomized population by treatment arm and overall. Summaries will include descriptive statistics for continuous and categorical measures. Patient characteristics may be presented include:

- age
- gender
- race
- ethnicity
- country
- years of education
- work status
- height
- body weight
- body mass index (weight (kg) / [height (m)]²)
- amyloid PET burden
- APOE4 carrier status (carrier [ε 2/ ε 4, ε 3/ ε 4, ε 4/ ε 4], noncarrier [ε 3/ ε 3, ε 2/ ε 2, ε 3/ ε 2])
- APOE4 genotype ($\varepsilon 2/\varepsilon 4$, $\varepsilon 3/\varepsilon 4$, $\varepsilon 4/\varepsilon 4$, no $\varepsilon 4$)
- AChEI and/or memantine use at baseline
- time since onset of first AD symptoms
- time since AD diagnosis
- having one or more first degree relatives with AD
- tobacco use
- alcohol use
- caffeine use
- MMSE

6.2. Appendix 2: Treatment Compliance

Because dosing occurs at study visits, patients who attend all visits and successfully receive donanemab infusions are automatically compliant with this treatment. Any infusion where 75% (approximately 60 mL, where the starting volume is 80 mL) or more of the infusion solution is given will be considered a complete infusion.

Summary statistics for treatment compliance will be provided for the total number of complete infusions received, duration of complete infusion, and volume of complete infusion by treatment arm in the treatment period.

6.3. Appendix 3: Concomitant Therapy

Prior medications are defined as those that stop before randomization (the day prior to the first administration of study drug). Concomitant medications are defined as prior medications being

taken in any time during the treatment period and follow-up period. A summary of concomitant medications that were used will be presented through frequencies and percentages for safety analysis set. If the start or stop dates of therapies are missing or partial to the degree that determination cannot be made of whether the therapy is prior or concomitant, the therapy will be deemed concomitant.

Medications will be coded using the World Health Organization (WHO) drug dictionary.

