## Primary estimand/coprimary estimand

The primary clinical question of interest is:

What is the reduction in the frequency of ARIA-E events at Week 24 in participants with early symptomatic AD treated with an alternative donanemab dosing regimen compared to the standard donanemab dosing regimen, regardless of discontinuation or interruption of donanemab dosing for any reason and regardless of change in background AD medication?

The estimand is described by the following attributes:

- **Population** Participants with early symptomatic AD
- Endpoint Occurrence of ARIA-E by Week 24
- **Treatment condition** 4 randomized treatment arms of donanemab with varying dosing schemes
- **Population-level summary** The relative reduction in proportion of participants with ARIA-E events in the alternative donanemab regimen compared to the standard donanemab regimen
- Intercurrent events "Discontinuation or interruption of donanemab dosing for any reason" and "change in background AD medication." No other intercurrent events are considered
- Estimand strategy Treatment policy. Data will be collected and analyzed regardless of postrandomization events in the first 24 weeks of the trial. This strategy will be implemented by a Bayesian logistic regression model
- Rationale for estimand The study primary objective is to evaluate the effect of alternative donanemab dosing regimens versus the standard donanemab dosing regimen on ARIA-E rate

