# 7.1.3. Rechallenge in Cases of Systemic Hypersensitivity or Infusion-related Reactions

Dosing rechallenge is contraindicated in participants that have experienced a suspected or possible anaphylactic reaction, a reaction involving 2 or more organ systems, for example, mucocutaneous, respiratory, cardiovascular, or gastrointestinal systems, that occurs very close to a prior dose (Sampson et al. 2006).

For systemic hypersensitivity reactions or IRRs, which are not suspicious for anaphylaxis, after review of the data, and at the investigator's discretion, the participant may be rechallenged.

If rechallenge is planned, the participant may be premedicated for subsequent doses at the investigator discretion and according to local practice guidelines. Any premedication given will be documented as a concomitant therapy.

Prior to initiating premedication or rechallenging, the investigator may consult with the Sponsor.

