#### Guidance if ARIA is present

If ARIA is present, repeat MRIs are recommended every 4 to 6 weeks until resolution of ARIA-E or stabilization of ARIA-H.

For asymptomatic or mild symptoms, the participant can be observed; for moderate symptoms associated with ARIA-E, the use of oral or IV steroids can be considered. In the case of severe symptoms associated with ARIA-E, it is recommended to hospitalize the participant for close observation and consider the use of IV steroids such as high-dose dexamethasone or a similar agent. See Manual of Operations and Section 7.1.2 for more guidance.

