#### 9.3.9.3. Prior and Concomitant Therapy

Prior medications are defined as those that stop before randomization (Visit 2).

Concomitant medications are defined as those being taken on or after randomization (Visit 2).

Prior and concomitant medications will be listed.

A summary of concomitant medications will be presented as frequencies and percentages for each treatment group. Medications will be coded using the World Health Organization drug dictionary.

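### SAP 6.3 builds its definition of concomitant medication on drugs that have already stopped, which contradicts itself and departs without explanation from Protocol 9.3.9.3

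*SAP*

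**What the plan says.** SAP 6.3 (Appendix 3: Concomitant Therapy) gives two definitions in succession. The first reads "Prior medications are defined as those that stop before randomization (the day prior to the first administration of study drug", with the bracket then closed. The second begins "Concomitant medications are defined as prior medications being" and continues over the page as "taken in any time during the treatment period and follow-up period". The sentence runs on grammatically across the page break, so nothing appears to be missing between the two halves.

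The same paragraph has a default rule. If missing or partial dates mean that a "determination cannot be made of whether the therapy is prior or concomitant", the therapy counts as concomitant. The paragraph asks for frequencies and percentages in the safety analysis set and does not mention treatment arm.

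Protocol 9.3.9.3 defines prior medications in the same way, by a stop before randomisation at Visit 2. For the other class it says "Concomitant medications are defined as those being taken on or after randomization (Visit 2". It places no condition on when the drug was started. It also promises a listing of both classes and a summary for each treatment group.

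**The concern.** A programmer working from SAP 6.3 has no usable rule. The second definition takes as its starting set drugs that are already over, then asks which of them were used on study.

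The drugs at risk of being left out are those first started after dosing began, and the protocol foresees several. Under its guidance for when ARIA is present, "for moderate symptoms associated with ARIA-E, the use of oral or IV steroids can be considered". On rechallenge after an infusion reaction, Protocol 7.1.3 states: "Any premedication given will be documented as a concomitant therapy". Protocol 6.9 allows symptomatic AD treatment to be started on study.

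The SAP reports ARIA-E duration by regimen (4.6.6) and compares infusion-related reactions between arms (4.5.3). A reader of those results would expect the concomitant-medication summary to show on-study drug use by arm. Built on the SAP wording, it would not do so reliably.

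**Working it through.** No sample size, power or event figure is involved. The check is on the logic of the definitions, followed by a comparison of the two documents.

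**Notation.** Let R be randomisation, s a drug's start and e its stop (e is later than any study date if the drug is ongoing). All dates are complete unless stated.

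**Step 1, SAP read literally.**
- Prior: e < R.
- Taken during treatment or follow-up: requires e ≥ R.
- Concomitant = prior and taken on study: e < R and e ≥ R. No drug satisfies both.

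**Step 2, SAP read loosely** (prior taken to mean started before R).
- Concomitant: s < R and e ≥ R.
- Left out: every drug with s ≥ R.

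**Step 3, Protocol 9.3.9.3.**
- Concomitant: e ≥ R, whatever s is. This is the set in Step 2 plus the drugs with s ≥ R.

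**Step 4, side by side.**

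| Drug | SAP, literal | SAP, loose | Protocol |
|---|---|---|---|
| Started and stopped before R | not concomitant | not concomitant | prior |
| Started before R, continued on study | not concomitant | concomitant | concomitant |
| Baseline AD drug, changed or stopped on study | not concomitant | concomitant | concomitant |
| First started on study | not concomitant | not concomitant | concomitant |
| Dates cannot settle the class | concomitant by default | concomitant by default | no rule stated |

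Neither SAP reading reproduces the protocol's set.

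**Step 5, is the departure explained?** SAP 4.1 says that changes to protocol methods, with their justification, will be described in the SAP and/or the clinical study report. SAP 6.3 gives no reason, and no entry in the SAP version history names this definition.

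**Step 6, the gloss on randomisation.** The Schedule of Activities puts randomisation and the first infusion both at Visit 2, Week 0. The SAP bracket refers to the day before first dosing and can be read two ways:
- It may date randomisation to that day, which disagrees with the Schedule. A drug stopped on that day would then fall into neither class.
- It may mean that the prior window runs up to and including that day, which agrees with the Schedule. Such a drug would then be prior.

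The wording does not say which is meant.

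**The case against.** The best defence is that this is a stray word. The SAP treats prior and concomitant as alternatives in its default rule, so two exclusive classes were evidently intended, and the protocol supplies the definition needed to separate them. A sensible programmer would probably follow the protocol. This is the likeliest explanation, but it does not remove the contradiction. The SAP is the document from which tables are programmed, and it should not depend on a guess at intent.

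Several stronger readings are tempting, and the documents do not support them.

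- **That the table will be empty, or will lose every on-study drug.** The default rule brings in therapies with undeterminable dates. On the loose reading, drugs continued from before randomisation are counted.
- **That rescue treatment becomes invisible.** Protocol 6.9 requires every medication to be recorded with reason, dates and dose. Treatment of infusion reactions is documented in addition to a dedicated reaction form. Protocol 9.3.9.3 promises a listing, and SAP 4.7 gives the DMC concomitant-medication listings for participants with ARIA.
- **That the named intercurrent event, change in background AD medication, can no longer be counted.** A frequency table counts users of a drug. It would not show how often treatment changed even under the protocol's definition. On the loose reading, baseline AD drugs later changed or stopped stay in the table and only new starts drop out. The estimand handles this event by treatment policy.
- **That the number of omitted steroid courses can be estimated.** The documents give no rate of steroid use. ARIA-E rates from the Phase 2 study cannot supply one for this trial's four regimens.
- **That the bracketed gloss creates a gap between the classes.** It does so on only one of the two readings in Step 6.

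**Conclusion.** The two definitions in SAP 6.3 cannot both be applied to a fully dated drug, and they conflict with Protocol 9.3.9.3 without explanation. This is a wrong rule in the analysis text and goes beyond missing detail. It rests on the wording alone and needs no numerical assumption.

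The consequence is small. One descriptive safety summary would be wrong if programmed as written. How wrong depends on which reading is adopted, and the documents give no figure from which to size it. The primary model takes no input from this summary, and the underlying records and the protocol's listing remain.

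Two lesser points in the same paragraph also need settling. The gloss on randomisation is ambiguous against the Schedule of Activities, and the by-arm presentation promised in the protocol is not carried into the SAP.

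**What to change.** In SAP 6.3:

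1. Delete *prior* from the definition of concomitant medication and restate the protocol rule. Concomitant is any medication taken on or after randomisation at Visit 2, whatever its start date. Prior is any medication stopped before Visit 2.
2. Remove the bracketed gloss on randomisation, or reword it to agree with the Schedule of Activities, where randomisation and first infusion share Visit 2.
3. State that the summary is presented by treatment arm, as Protocol 9.3.9.3 already says.
4. Keep the default rule for missing or partial dates.

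The cost is a few words in the SAP. The Schedule of Activities already collects concomitant medications at every visit, so no new data are needed. The change returns the SAP to the protocol's own rule, so no protocol amendment should be required.

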6.4. Appendix 4: Multicenter Studies

This study will be conducted by multiple investigators at multiple sites internationally. In case any investigator has an inadequate number of subjects (defined as 1 or 0 randomized subjects per treatment group) for the planned analyses, the following strategy will be implemented. Data from all such investigators will be pooled. The pooling will be done first within a country. If the resulting pool within a country is still inadequate (1 or 0 randomized subjects to 1 or more treatment arms), no further pooling will be performed. A listing including country, investigator site with address, number of patients enrolled (randomized) by each site, and unique patient IDs will be presented.

6.5. Appendix 5: Handling Missing Data from Participant Dropouts

Because AACQ study follows a patient population that is elderly with multiple comorbidities for 76 weeks, patient withdrawal is of particular concern. Additional efforts will be undertaken to reduce patient withdrawals and to obtain information on patients who are initially categorized as lost to follow-up.

A likelihood-based mixed effects model for repeated measures will be used to handle missing data for biomarker analyses. The model parameters are simultaneously estimated using restricted likelihood estimation incorporating all the observed data. Estimates have been shown to be unbiased when the missing data are missing at random and when there is ignorable non-random missing data.

Repeated measures analyses will only use data from visits where the data was scheduled to be collected (Andersen and Millen 2013). When patients discontinue early from the study, there may be safety or biomarker measurements at visits where the variables were not scheduled to be collected. This data will be used in all other analyses.

7. References

Andersen SW and Millen BA. On the practical application of mixed effects models for repeated measures to clinical trial data. *Pharm Stat.* 2013;12(1):7-16.

Integrated Statistical Analysis Plan (LY3002813): Assessment of safety of LY3002813 in early symptomatic Alzheimer's disease. 2023.

Protocol (I5T-MC-AACQ): Investigating the effect of different donanemab dosing regimens on ARIA-E and amyloid lowering in adults with early symptomatic Alzheimer's disease. 2022.

Wang F and Gelfand EG. A simulation-based approach to Bayesian sample size determination for performance under a given model and for separating models. *Stat Sci.* 2002;17(2):193-208.

Signature Page for VV-CLIN-160476 v1.0

Approval	PPD
	29-Jul-2024 19:37:24 GMT+0000

Signature Page for VV-CLIN-160476 v1.0
